5.2 Subject enrollment and randomization and initiation of investigational product

5.2.1 Procedures for randomization

Subjects will be proceeded to visit 2-baseline visit (study drug 1) after they pass the screening visit (visit 1).

Randomization to dapagliflozin or glimepiride: After signing informed consent, confirming eligibility and completion of baseline assessments (visit 2), subjects will be randomized in a 1:1 fashion to either open-label dapagliflozin 5 mg daily or open-label glimepiride 2 mg daily for 4 weeks and escalate the dose gradually up to dapagliflozin 10 mg daily or glimepiride 4 mg daily (no more than 4 mg daily) as needed based on their glucose monitoring. Patients will be asked to check glucose in the morning and before dinner. Fasting glucose should be between 80-130 mg/dl and daytime glucose should be in the range of 80-160 mg/dl.

Procedure for Subject Treatment Assignment: Subjects will be randomized to treatment with either dapagliflozin or glimepiride. The procedures for randomization will be determined by the study biostatistician. The study drugs will be dispensed by the research pharmacy.

5.2.2 Study Visits

The schedule of study visits is shown in Table 1. After obtaining informed consent, verifying eligibility at screening and completing all required baseline assessments, subjects will be randomized and provided with study medications. Patients will be also followed every 4 weeks in each study drug period. The staff should query the subject regarding any changes to their health, changes to their medication regimen, and frequency and severity of hypoglycemia at each visit.

Visit 1: Screening/Eligibility (Day -30 to 0)

An eligibility visit will be scheduled for subjects who, based on preliminary screening (telephone, email, medical chart review), meet the general entry criteria (refer to inclusion criteria). At Visit 1 the investigator or her designee will obtain written informed consent, after which all required eligibility examinations will be performed. The eligibility examination will include the following laboratory assessments: Hemoglobin A1c (HbA1c), comprehensive metabolic panel (CMP) including FBG, complete blood count with platelets (CBCP), thyroid stimulating hormone (TSH), lipid profile, B type natriuretic peptide (BNP), urine albumin assessment, urine analysis and in all women of child bearing age and potential, a urine pregnancy test, even if an accepted method of contraception is being used. If any of the required laboratory measures are documented in the subject's medical record as being completed in the prior 3 months (1 month for HbA1c, and 6 months for urine albumin), they will not need to be repeated at the screening visit.

Weight, height and seated blood pressure and pulse will be obtained. A structured history and physical examination and electrocardiogram will be performed at the screening visit. All visit 1 measures are to be completed at one visit.

Visit 2- Baseline Visit (Study Drug 1) (Day 0)

This study will include CAN assessments (see section 5.2.3), meter download for evaluation of hypoglycemia at baseline and to initiate treatment with either dapagliflozin or glimepiride.

Upon satisfactory completion of all eligibility and baseline visit (study drug 1) assessment, a 12-week supply of dapagliflozin 5 mg tablet or glimepiride 2 mg tablet will be provided, and written instructions for use of the medication reviewed with and provided to the subject. Subjects will be instructed to take dapagliflozin 5 mg daily or glimepiride 2 mg daily with or without food in the morning once daily for 4 weeks then escalating the dose up to dapagliflozin 10 mg daily or glimepiride 4 mg (no more than 4 mg daily) as needed based on glucose monitoring and control. Participants will be instructed to monitor glucose 2 times

daily, fasting glucose and before dinner with the goal of fasting glucose between 80-130 mg/dl and of pre-meal glucose between 80-180 mg/dl. Participants will be asked to record glucose data and the number of doses taken every day on a log that will be provided. Participants will be also asked to bring a glucometer with them for each visit. Subjects are to be reminded to return any unused study medication at their next visit. Adverse events will be recorded and reported as required.

Study staff will contact the subject within one week of the Visit 2 to assess medication compliance and tolerance.

All subjects in group A and B will be allocated and randomized to each treatment sequence in a 1:1 fashion. Participants will receive either dapagliflozin 5 mg or glimepiride 2 mg daily initially for 4 weeks then titrating the dose based on blood glucose levels up to dapagliflozin 10 mg daily or glimepiride 4 mg (no more than 4 mg daily) for 8 more weeks (total 12 weeks) followed by a 2-week washout period. Participants will then receive the study drugs in reverse order to the first study drug period during second crossover period for another 12 weeks.

Visit 3: Safety Monitoring (Study Drug 1) (Week 4)

At this visit, the study staff will obtain vital signs (weight, blood pressure, resting heart rate) and will ask the subject about any changes in health status or physical symptoms and record the findings in the source documents. Glucometers will be downloaded and incidence of hypoglycemia will be evaluated. The staff will assess compliance with study drug and tolerance. Adverse events will be recorded and reported as required.

Visit 4: Safety Monitoring (Study Drug 1) (Week 8)

At this visit, the study staff will obtain vital signs (weight, blood pressure, resting heart rate) and will ask the subject about any changes in health status or physical symptoms and record the findings in the source documents. Glucometers will be downloaded and incidence of hypoglycemia will be evaluated. The staff will assess compliance with study drug and tolerance. Adverse events will be recorded and reported as required. Urine pregnancy testing may be performed at the discretion of the investigator for all women of childbearing potential.

Participants will be provided with a Freestyle Libre Pro CGM to collect glucose data for 2 weeks following this visit. Libre Pro CGM will be placed on the participants by trained study personnel during this visit. Freestyle Libre Pro CGM is very simple to use and does not require glucose calibration or participant's operation. Then participants will also be asked either to mail the CGM or to bring the CGM with them in next visit.

Visit 5: End of Study Drug 1 (Week 12)

At this visit, the following will be performed: vital signs (weight, blood pressure, resting heart rate), a structured history and physical examination, electrocardiogram, information about any adverse events, all CAN assessments (see section 5.2.3), meter

download for evaluation of hypoglycemia, blood draw for HbA1c, BNP, and safety laboratory assessments (CMP including FBG, CBCP, urine albumin assessment and lipid profile). The study staff will collect any unused study medication. The number of unused dapagliflozin or glimepiride tablets will be recorded in the source document and unused medication secured until returned for final drug disposition. During this visit, the site where a CGM sensor has been worn will be carefully assessed by study personnel.

Wash-out period

A 2-week wash-out period will be followed after first study drug period.

Visit 6: Baseline Visit (Study Drug 2) (Week 15)

At this visit, the following will be performed: vital signs (weight, blood pressure, resting heart rate), a structured history, information about any adverse events, electrocardiogram, all CAN assessments (see section 5.2.3), meter download for evaluation of hypoglycemia and blood draw for BNP. The key activity of this visit is to re-initiate treatment with either dapagliflozin or glimepiride. After a 2-week wash-out period, visit 6-baseline visit (study drug 2) will be initiated. Participants will again receive study drugs (dapagliflozin or glimepiride) in a reverse order to the first study drug period for another 12 weeks. Urine pregnancy testing may be performed at the discretion of the investigator for all women of childbearing potential.

A 12-week supply of dapagliflozin 5 mg tablet or glimepiride 2 mg tablet will be provided, and written instructions for use of the medication reviewed with and provided to the subject. Subjects will be instructed to take dapagliflozin 5 mg or glimepiride 2 mg with or without food in the morning daily for 4 weeks then escalating to dapagliflozin 10 mg daily or glimepiride 4 mg (no more than 4 mg daily) as needed based on glucose monitoring and control. Participants will be asked to record the number of doses taken every day on a log that will be provided. Subjects are to be reminded to return any unused study medication at their next visit.

Study staff will contact the subject within one week of the Visit 6 to assess medication compliance and tolerance.

Visit 7: Safety Monitoring (Study Drug 2) (Week 19)

At this visit, the study staff will obtain vital signs (weight, blood pressure, resting heart rate) and will ask the subject about any changes in health status or physical symptoms and record the findings in the source documents. Glucometers will be downloaded and incidence of hypoglycemia will be evaluated. The staff will assess compliance with study drug and tolerance. Adverse events will be recorded and reported as required.

Visit 8: Safety Monitoring (Study Drug 2) (Week 23)

At this visit, the study staff will obtain vital signs (weight, blood pressure, resting heart rate) and will ask the subject about any changes in health status or physical symptoms and record the findings in the source documents. Glucometers will be downloaded and incidence of hypoglycemia will be evaluated. The staff will assess compliance with study drug and tolerance. Adverse events will be recorded and reported as required. Urine pregnancy testing may be performed at the discretion of the investigator for all women of childbearing potential.

Participants will be provided with a Freestyle Libre Pro CGM to collect glucose data for 2 weeks following this visit. A Libre Pro CGM will be placed on the participants by trained study personnel during this visit. Freestyle Libre Pro CGM is very simple to use and does not require glucose calibration or participant's operation. Then participants will also be asked either to mail the CGM or to bring the CGM with them in next visit.

Visit 9: End of Study Drug 2 (Week 26) or Final Visit

At this visit, the following will be performed: vital signs (weight, blood pressure, resting heart rate), a structured history and physical examination, information about any adverse events, electrocardiogram, all CAN assessments (see section 5.2.3), meter download for evaluation of hypoglycemia, blood draw for HbA1c, BNP, and safety laboratory assessments (CMP including FBG, CBCP, urine albumin assessment and lipid profile). The study staff will collect any unused study medication. The number of unused dapagliflozin or glimepiride tablets will be recorded in the source document and unused medication secured until returned for final drug disposition.

The study staff will collect any unused study medication. The number of unused dapagliflozin or glimepiride tablets will be recorded in the source document and unused medication secured until returned for final drug disposition. The subjects will be again assessed for adverse events.

During this visit, the site where a CGM sensor has been worn will be carefully assessed by study personnel.

Within 1 week of the final visit, the study staff will contact the subject by phone or email to inquire about any changes in health status.

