4.2 Exclusion criteria

Subjects should not enter the study if any of the following exclusion criteria are fulfilled:

1. History of recurrent urinary tract infections
2. Patients with mycotic infections especially genital infection.
3. Severely hypotensive patients
4. History of unexplained microscopic or gross hematuria, or microscopic hematuria at visit 1, confirmed by a follow-up sample
5. Presence of hypersensitivity to dapagliflozin or other SGLT2 inhibitors (e.g. anaphylaxis, angioedema, exfoliative skin conditions)
6. Inability or refusal to comply with protocol
7. Current participation or participation in an experimental drug study in previous three months
8. Presence of history of diabetic ketoacidosis
9. Planned cardiac surgery or angioplasty within 3 months
10. Recent history of acute CV events such as MI, stroke, PAD within 3 months prior to enrollment
11. Patients with severe renal impairment or unstable or rapidly progressing renal disease or end stage renal disease.
12. Clinical conditions that could interfere with the cardiovascular autonomic function and heart rate variability (arrhythmias)
13. Severe hepatic insufficiency and/or significant abnormal liver function (defined as aspartate aminotransferase $>3\times$ upper limit of normal (ULN) and/or alanine aminotransferase $>3\times$ ULN) or creatinine kinase $>3\times$ ULN.
14. History of cancer other than basal cell carcinoma and or treatment for cancer within the last 5 years
15. Women of child-bearing potential who may be pregnant or lactating.
16. History of pancreas, kidney or liver transplant.

17. History of drug or alcohol abuse within 5 years
18. History of allergy to sulfa drugs
19. Presence of any condition that, in the opinion of the investigator would make it unlikely for the subject to complete the study.
20. Congestive heart failure (CHF) defined as New York Heart Association class III and IV

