13. IMPORTANT MEDICAL PROCEDURES TO BE FOLLOWED BY THE INVESTIGATOR

Given the mechanistic nature of the study drug, dapagliflozin, the common side effects are urinary tract infection (UTI) and genital mycotic infection. Those patients who developed infections will be managed according to standard care and guidelines. Baseline urinary analysis (UA) will be collected before starting any study medications. In any case of suspect UTI, UA will be collected. If positive urine analysis, then we will proceed with urine culture and treat the patient accordingly to bacterial growth in the urine culture. If negative UA, we will not proceed with midstream urine culture.

If the patient has abnormal ECG, the study investigator will ask the prior documented ECG report from patient's primary care provider or endocrinologist and repeat the ECG. If the patient is symptomatic, then patient will be sent to emergency department for further urgent evaluation of coronary artery disease. The study medication will be discontinued. If asymptomatic, then the investigators will ask the prior ECG report and repeat ECG in the same visit. If similar findings compared to the old one, then he will be monitored conservatively. If significant changes from prior ECG, then he will be referred to the cardiologist for further evaluation upon the investigator's discretion.

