13.2.1 Maternal exposure

Dapagliflozin is pregnancy category drug C. Based on the results of reproductive and developmental toxicity studies in animals, dapagliflozin doses > 137 MRHD may affect renal development and skeletal malformation and maturation.

Glimepiride is pregnancy category drug C. There are no adequate and well-controlled studies in pregnant women. In animal studies there was no increase in congenital anomalies, but an increase in fetal deaths occurred in rats and rabbits at glimepiride doses 50 times (rats) and 0.1 times (rabbits) the maximum recommended human dose (based on body surface area).

As soon as we learn that a female subject has been pregnant, we will stop the study medication immediately. We will report this to AstraZeneca and IRBMED immediately. Patient will be asked to follow with her Obstetrician closely. We will also follow the pregnancy outcomes and report this to AstraZeneca.

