BASELINE VISIT DATE: _____

Comments:

Signature of Coordinator: _____ Date: _____

Visit 2 Overview

SUBJECT ID: _____

Date: _____

Weight (kgs): _____ Blood Pressure (seated): _____

Pulse (seated): _____ Resting HR (supine from HRV): _____

Height (inches): _____

Assessments

- | | |
|--|---------------------|
|  HRV Testing | Performed by: _____ |
|  CARTs Testing | Performed by: _____ |
|  Assess Hypoglycemia | Performed by: _____ |
|  Medication Dispensing | Performed by: _____ |
|  Adverse Events Monitoring | Performed by: _____ |

Urine Pregnancy Test Completed for Women and Result:

- Negative Positive Not Done Not Applicable

VISIT 3 Scheduled for: _____

Comments:

Signature of Coordinator: _____ Date: _____

Visit 3 Overview

SUBJECT ID: _____ Date: _____

Weight (kgs): _____ Blood Pressure (seated): _____

Pulse (seated): _____ Resting HR (supine 5 mins): _____

Height (inches): _____

Assessments

Assess Hypoglycemia Performed by: _____

Medication Compliance Performed by: _____

Adverse Events Monitoring Performed by: _____

Urine Pregnancy Test Completed for Women and Result:

Negative Positive Not Done Not Applicable

VISIT 4 Scheduled for: _____

Comments:

Signature of Coordinator: _____ Date: _____

Visit 4 Overview

SUBJECT ID: _____ Date: _____

Weight (kgs): _____ Blood Pressure (seated): _____

Pulse (seated): _____ Resting HR (supine 5 mins): _____

Height (inches): _____

Assessments

Assess Hypoglycemia Performed by: _____

Medication Compliance Performed by: _____

Adverse Events Monitoring Performed by: _____

Urine Pregnancy Test Completed for Women and Result:

Negative Positive Not Done Not Applicable

VISIT 5 Scheduled for: _____

Comments:

Signature of Coordinator: _____ Date: _____

Visit 5 Overview

SUBJECT ID: _____ Date: _____

Weight (kgs): _____ Blood Pressure (seated): _____

Pulse (seated): _____ Resting HR (supine 5 mins): _____

Height (inches): _____

Assessments

Medical History and Physical Examination Performed by: _____

Laboratory Measures Performed by: _____

HRV Performed by: _____

CARTs Testing Performed by: _____

Medication Compliance Performed by: _____

Adverse Events Monitoring Performed by: _____

Assess Hypoglycemia Performed by: _____

EKG Performed by: _____

Urine Pregnancy Test Completed for Women and Result:

Negative Positive Not Done Not Applicable

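### The 3-month chart waiver in section 5.2.2, as written, covers the urine pregnancy test and urinalysis, against the passages that place both at Visit 1, and no repeat pregnancy test is mandated before either drug starts

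*Combined protocol and SAP*

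**What the plan says.** **The waiver.** In section 5.2.2, the list of laboratory assessments for Visit 1 closes as follows (final word omitted): "urine analysis and in all women of child bearing age and potential, a urine pregnancy test, even if an accepted method of contraception is being". The sentence that follows opens "If any of the required laboratory measures are documented in the subject's medical record as being completed in the prior 3 months" and then sets the exceptions and the effect: "1 month for HbA1c, and 6 months for urine albumin), they will not need to be repeated at the screening visit". Neither urine test has its own look-back period, so both fall under the 3-month default.

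**Passages that place the urine tests at Visit 1.**
- Table 1 marks the combined urinalysis and pregnancy-test row at Visit 1 and nowhere else.
- Section 6.4.4 says both tests are obtained at the screening visit and mentions no waiver.
- Exclusion 4 depends in part on blood found in the Visit 1 urine and checked on a second sample.
- Section 13 says: "Baseline urinary analysis (UA) will be collected before starting any study medications".

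**Later pregnancy testing.** The Visit 2 text asks for none. At Visit 6, when the second drug starts, the wording is "Urine pregnancy testing may be performed at the discretion of the investigator for all women of childbearing potential", and Visits 4 and 8 are worded the same way. The form for every visit from 1 to 9 prints the line "Urine Pregnancy Test Completed for Women and Result", with Not Done among the permitted answers.

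**The criterion concerned.** Exclusion 15 reads: "Women of child-bearing potential who may be pregnant or lactating".

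**The concern.** The look-back was varied test by test, and the pregnancy test was left at the default. Three months is a reasonable age for a lipid panel or a blood count. It says little about current pregnancy, and a urinalysis of that age is not a Visit 1 finding.

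Two things are at stake. One is eligibility and participant safety: a site relying on the waiver could judge exclusion 15 on an old result, although section 13.2.1 itself reports animal renal and skeletal findings for dapagliflozin and fetal deaths for glimepiride. The other is the urinary baseline. Exclusion 4 needs a Visit 1 result, and urinary tract infection is a named safety objective in section 2.3, so an old urinalysis makes it harder to tell an existing abnormality from one arising on drug.

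**Working it through.** The plan states no maximum age for either test, so there is no figure to reproduce. The ages follow from its own windows.

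**Inputs**
- W, chart look-back: 3 months (section 5.2.2). The conversion to 91 days, range 90 to 92, is an assumption.
- S, screening to first dose: 0 to 30 days (Visit 1 in section 5.2.2, Table 1; the Visit 1 form also says 30 days). Section 6.2.1 says 4 weeks, or 28 days.
- P, first drug to second drug: 12 weeks of treatment plus 2 of wash-out, 14 × 7 = 98 days. This agrees with the 26-week design, since 12 + 2 + 12 = 26. Table 1 labels Visit 6 as Week 15; read as elapsed weeks, that is 15 × 7 = 105 days.
- Visit window: ±7 days (Table 1).
- Months are days / 30.44.

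**Waiver used, oldest permitted result, no discretionary test**
- Age at first dose = W + S = 91 + 30 = 121 days (120 to 122), or 4.0 months. With the 4-week wording: 91 + 28 = 119 days. With the Visit 2 window added: 121 + 7 = 128 days.
- Age at second drug = W + S + P = 121 + 98 = 219 days (218 to 220), or 7.2 months. With Week 15 taken as elapsed: 121 + 105 = 226 days, or 7.4 months. With 7 more days for the visit window: 233 days.

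**Test done at Visit 1 (W = 0)**
- Age at first dose = 0 to 30 days, or 37 with the window.
- Age at second drug = 98 + 0 to 98 + 30 = 98 to 128 days, or 135 with the window.

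**What the waiver contributes.** It supplies 91 of the 121 days at first dose (91/121 = 75%) and 91 of the 219 at the second drug (91/219 = 42%). Closing it therefore settles most of the first-dose problem. The remaining interval of up to 128 days before the second drug comes from the visit schedule.

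**Whether another passage closes the gap.** The result line on the Visit 2 and Visit 6 forms does not, because Not Done is an accepted answer. The exclusion checklist on the screening form does not either, because it omits pregnancy and lactation. The nearest items are a contraception tick-box among the inclusion criteria and the Visit 1 test line, which also accepts Not Done.

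**The case against.** The strongest reply is that the waiver was never meant to reach the pregnancy test. Section 5.2.2 asks for it even in women using contraception. The screening form lists laboratory measures and the pregnancy test as separate items. Section 6.4.4 and Table 1 put the test at Visit 1. This is good evidence of intent, but it does not change the sentence, which follows directly on a list of laboratory assessments that includes the test. A coordinator could read it either way. Treating section 5.2.2 as a permitted exception to section 6.4.4 does not help, because the old result is then allowed.

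The second reply is that other safeguards exist. Contraception is required (sections 5.1 and 13.2, and the screening checklist), staff ask about health changes at each visit, tests are optional at Visits 4, 6 and 8, and every visit form carries a prompt. These lower the risk and stand as mitigation. None of them verifies status.

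On urinalysis, section 13 calls for a new sample whenever a urinary infection is suspected, and section 6.4.3 records conditions present before the first dose as baseline. That limits the harm to safety attribution. It does not supply the Visit 1 result that exclusion 4 needs.

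The 4- and 7-month figures also combine every worst case, and the documents do not say how many of the 45 participants would be women of childbearing potential. Both points are fair: the figures are upper bounds, not expected values.

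**Conclusion.** The point holds as a contradiction in the eligibility and safety text. As written, the waiver allows a pregnancy result about 121 days old at first dose and about 219 days old at the second drug. This assumes that the waiver is used with the oldest permitted result, that the full screening window is taken, and that no discretionary test is done. The sample size and the primary analysis are not affected.

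Four stronger readings are tempting, and the documents do not support them:
- **That no test is required before either drug.** A Visit 1 pregnancy test is required unless waived, and section 13 calls for a baseline urinalysis. What is missing is a mandated repeat pregnancy test at Visit 2 or Visit 6.
- **That the waiver conflicts with section 13.2.1.** That section says "As soon as we learn that a female subject has been pregnant, we will stop the study medication immediately". It acts once a pregnancy is known and sets no testing frequency.
- **That exclusion 15 is defeated.** It bars women who may be pregnant and is not tied to a test result, so a suspected pregnancy excludes whatever the age of the test.
- **That tests at Visits 2 and 6 must be made mandatory.** The plan expressly chose discretion at Visit 6. How often to test is the sponsor's clinical decision.

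**What to change.** 1. Reconcile the waiver sentence in section 5.2.2 with section 6.4.4, Table 1, exclusions 4 and 15 and section 13, so that it no longer overrides the Visit 1 urine tests those passages call for.
2. Reconcile Table 1 (Visit 1 only), the discretionary wording at Visits 4, 6 and 8, and the pregnancy-test line on the visit forms with its Not Done option, so that the documents state one schedule. The sponsor decides what that schedule is.

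The cost is small: a wording change in section 5.2.2, and matching edits to Table 1 and the forms where needed. The downside is that a few screening urine tests can no longer be taken from the chart.

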3. STUDY PLAN AND PROCEDURES

3.1 Overall study design and flow chart

This is a 26-week, single-center, randomized, single-blinded to the investigators, open-label, 2-period crossover phase IV clinical trial comparing 12-weeks of glycemic intervention with dapagliflozin versus glimepiride on measures of HRV. The two periods will be separated by a 2-week wash-out period. All subjects will be allocated and randomized to each treatment sequence in a 1:1 fashion. Participants will receive either dapagliflozin 5 mg or glimepiride 2 mg daily initially for 4 weeks then titrating the dose gradually up to dapagliflozin 10 mg daily or glimepiride 4 mg daily (no more than 4 mg daily) as needed based on glucose monitoring for 8 more weeks (total 12 weeks) followed by 2-week washout period. Then they will receive the study drugs in reverse order to the first period for another 12 weeks. Glucose variability will be also assessed using Abbott's Freestyle Libre Pro CGM for 2-week during each intervention period.

Figure 1: Proposed study design

[figure not shown]

Table 1: Proposed visit schedule

	Period 1					Wash-out	Period 2			
Visit Numbers	Visit 1	Visit 2	Visit 3	Visit 4	Visit 5		Visit 6	Visit 7	Visit 8	Visit 9
Visit Description	Screening	Baseline Visit (Study Drug 1)	Monitoring	Monitoring	End of Study Drug 1	N/A	Baseline Visit (Study Drug 2)	Monitoring	Monitoring	End of Study Drug 2
Time point	Day -30 to 0	Day 0	Week 4	Week 8	Week 12	Week 13-14	Week 15	Week 19	Week 23	Week 26
Visit window	1 month	± 7 days	± 7 days	± 7 days	± 7 days	NA	± 7 days	± 7 days	± 7 days	± 7 days
Informed consent and HIPPA ¹	X									
Medical history	X				X		X			X
Physical exam ²	X				X					X
Inclusion/Exclusion criteria	X									
Concomitant medications	X						X			
Vital signs	X	X	X	X	X		X	X	X	X
Urine analysis, urine β-HCG test in women of childbearing age	X									
Venous blood A1C	X				X					X
CBCP, FBG, comprehensive metabolic profile, , lipid profile, and urine albumin excretion	X				X					X
TSH	X									
BNP	X				X		X			X

ECG	X				X		X			X
HRV		X			X		X			X
CARTs		X			X		X			X
CGM				2 weeks					2 weeks	
Assess hypoglycemia		X	X	X	X		X	X	X	X
Record Adverse Events (AEs), Serious Adverse Events (SAEs)		X	X	X	X			X	X	X
Assessment of compliance by counting pills			X	X	X			X	X	X

¹ The informed consent form must be signed before any study procedure is performed.

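### The visit-week labels in Table 1 and the Visit 6 to 9 headings mix conventions, so the nominal timing of the Period 2 primary measurement is ambiguous (11 or 12 weeks on drug)

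*Combined protocol and SAP*

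**What the plan says.** The durations in the text are consistent. Section 3.1 describes the study as follows: "This is a 26-week, single-center, randomized, single-blinded to the investigators, open-label, 2-period crossover phase IV clinical trial". It adds that "The two periods will be separated by a 2-week wash-out period". In Section 5.2.2 the washout paragraph says "A 2-week wash-out period will be followed after first study drug period", and the Visit 6 paragraph says "After a 2-week wash-out period, visit 6-baseline visit (study drug 2) will be initiated", with the drugs then given "in a reverse order to the first study drug period for another 12 weeks". Section 5.5.2 repeats 12 weeks, 2 weeks and 12 weeks. The opening of Section 5.2.2 and Section 6.2.2 both set follow-up at 4-week intervals within a period.

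The visit labels are in Table 1 and again in the Section 5.2.2 headings. Visits 2 to 5 are at Day 0 and Weeks 4, 8 and 12. Visits 6 to 9 are at Weeks 15, 19, 23 and 26; for example, "Visit 6: Baseline Visit (Study Drug 2) (Week 15" and "Visit 8: Safety Monitoring (Study Drug 2) (Week 23" (closing bracket omitted in both), and "Visit 9: End of Study Drug 2 (Week 26) or Final Visit". Table 1 labels the washout column as Weeks 13 to 14 and gives Visits 2 to 9 a window of ±7 days.

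Sections 6, 12.2 and 12.3 define the primary outcome as the change in the LF:HF ratio from baseline to 12 weeks on each drug.

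**The concern.** The visit table sets when the primary endpoint is measured. Period 1 counts elapsed weeks from Day 0. If staff count the Period 2 labels the same way, they start the second drug 3 weeks after Visit 5 and test heart rate variability 11 weeks later. The two halves of each patient's contrast would then have different nominal times on drug, although the endpoint is defined at 12 weeks for both. The stated dose sequence (4 weeks, then 8 more) would become 4 and 7.

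The labels also affect the exploratory glucose analysis. The sensor is worn for the 2 weeks after Visits 4 and 8, so its distance from the heart rate variability test would differ between periods.

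**Working it through.** **Inputs.** Visit labels: Table 1 and the Section 5.2.2 headings. Durations: Sections 3.1, 5.2.2 and 5.5.2. Visit spacing: Sections 5.2.2 and 6.2.2.

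**1. The plan's own total.** 12 + 2 + 12 = 26 weeks, which reproduces the stated study length. It does not discriminate, because 12 + 3 + 11 = 26 as well.

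**2. Differences between labels under each convention.**

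| Reading | Period 1 | Gap, Visit 5 to 6 | Period 2, Visit 6 to 9 | Visit 8 to 9 | Total |
|---|---|---|---|---|---|
| Stated in the text | 12 | 2 | 12 | 4 | 26 |
| Elapsed weeks for all visits | 12 | 15 − 12 = 3 | 26 − 15 = 11 | 26 − 23 = 3 | 26 |
| Start of the numbered week for all visits | 11 | 3 | 11 | 3 | 25 |
| Mixed: Visits 6 to 8 at start of week, the others at elapsed weeks | 12 | 14 − 12 = 2 | 26 − 14 = 12 | 26 − 22 = 4 | 26 |

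No single convention reproduces the text. Only the mixed reading does. It also fits the washout column: Weeks 13 and 14 are two numbered weeks, and Weeks 15 to 26 counted inclusively are 26 − 15 + 1 = 12.

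**3. Size if the labels are read literally.**

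- Time on the second drug: 11 × 7 = 77 days against 12 × 7 = 84, which is 7/84 = 8% shorter.
- Gap between drugs: 21 days against 14.
- Sensor end to heart rate variability test: Period 1, 12 − (8 + 2) = 2 weeks; Period 2, 26 − (23 + 2) = 1 week.
- Windows, measured from the actual first dose: Period 1, 12 ± 1 = 11 to 13 weeks; Period 2, 11 ± 1 = 10 to 12 weeks. If both the baseline and the end visit may move by 7 days, the ranges are 10 to 14 and 9 to 13.

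**4. Effect on the treatment contrast.** Let δ be the difference between drugs at 12 weeks, p an additive shift between periods, and nA and nB the sequence sizes, with N = nA + nB. The within-patient difference has mean δ + p in one sequence and δ − p in the other. The unadjusted paired mean is therefore δ + p(nA − nB)/N. With equal sequences the shift cancels from the mean. A model with a period term removes it in either case.

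An additive shift does not cover an effect that is still growing at week 11. Assume, for illustration only, linear growth to week 12, so that each drug shows 11/12 of its 12-week effect when given second. With balanced sequences the contrast becomes δ × (1 + 11/12)/2 = δ × 23/24. For the planning difference of 1.4 this is 1.34, about 4% less. With 38 patients, and 2.1 taken as the within-person SD so that the SD of the paired difference is 2.1 × √2 = 2.97, power is 0.81 at 1.4, in line with the stated 80%. It is 0.77 at 1.34. A period term does not undo this attenuation. If the effect has levelled off before week 11, the loss is about nil.

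**The case against.** The best reply is that the intended schedule is clear. The 2-week washout and the 12-week second period are each stated several times, including in the Visit 6 paragraph itself, which also provides a 12-week supply. The washout column spans two numbered weeks. This is a single-center study, and the visit overview pages of the case report form carry no week numbers. A reader might infer from the Visit 6 to 9 labels that the trial was designed with a 3-week washout and an 11-week second period. The documents do not support that inference; this evidence points to start-of-week labels for Visits 6 to 8 and an end-of-week label for Visit 9. That part of the reply stands.

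The second reply is that the result is protected. Sequences are allocated 1:1, Section 12.2 names a mixed model with treatment, sequence and period effects as a corresponding primary analysis, and a ±7-day window is as wide as the discrepancy. The dispensing form records the date the drug was started and the heart rate variability report is dated, so actual time on drug can be derived. This largely stands for an additive shift.

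Two things remain. A window permits scatter around a target and does not move a target that is a week off. The mixed convention is stated nowhere, and Visits 3 to 5 do not follow it.

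**Conclusion.** The inconsistency is real: under any single week convention the labels give a 3-week gap, an 11-week second period and a 3-week last interval, against the stated 2, 12 and 4 weeks. It is most likely a labelling slip. It still deserves correction, because the affected figures fix the nominal time of the primary measurement and the correction is nearly free.

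The likely effect on the treatment contrast is small: about nil if the drug effects have levelled off by week 11, and about 4% (1.4 to 1.34, power 0.81 to 0.77) under linear growth to week 12 with visits booked literally. The documents do not say which pattern applies. One might go further and say that the paired t-test is biased by the period difference. That does not follow from the plan: with balanced sequences an additive shift cancels from the mean. A residue of p(nA − nB)/N arises only if the sequences are unequal among patients with data in both periods, which is the primary analysis set of Section 12.1.1. The 1-week against 2-week sensor gap bears on exploratory analyses only.

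**What to change.** Reconcile Table 1 (time-point row and washout column) and the Visit 6 to 9 headings in Section 5.2.2 with the washout, period-length and visit-spacing statements in Sections 3.1, 5.2.2, 5.5.2 and 6.2.2. Use one week convention and state it in a table footnote, for example whether a label means elapsed weeks from the first dose of the study or of the period. The nominal timing of the primary endpoint should then be unambiguous in both periods. Which schedule is intended is for the sponsor to say; none is prescribed here.

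No new data collection or analysis is needed. The period term is already planned, and actual days from first dose to the heart rate variability test can be derived from dates already on the forms. The cost is an edit to one table and four headings.
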